## **2. Study Objectives**

**Specific Aim 1:** Conduct a 10-week placebo-controlled trial of bupropion 300 mg/day in 360 pregnant smokers who are at 13–26 weeks gestation. We will monitor smoking behavior and adverse effects (AEs) of the medication during a 10-week treatment period, with follow up for

CONFIDENTIAL

the remainder of the pregnancy (measuring length of gestation, rate of pregnancy complications, and birth outcomes). We will also provide two booster counseling sessions at weeks 2 and 6 postpartum and a final research evaluation at 24 weeks post-TQD. We will use text messages to send pregnancy-relevant information and medication-adherence cues based on their demonstrated ability to improve adherence in various populations (e.g., 22, 23). We hypothesize that:

**H1:** Bupropion-treated women will have a greater rate of biochemically confirmed cigarette abstinence than placebo-treated women.

**H2:** There will be no significant differences between treatment arms in the frequency of severe treatment-related AEs.

**H3:** Bupropion treatment will result in a higher birth weight than placebo.

**Specific Aim 2:** Assess changes in depression symptoms and craving as mediators of bupropion's effect on quit rates.

**Exploratory Aim:** Explore genetic, metabolic, and social/behavioral moderators of the efficacy of bupropion on cigarette abstinence and safety. To generate new hypotheses, we will explore whether the risk of AEs and the efficacy of bupropion treatment (vs. placebo) is moderated by: 1) the rate of nicotine metabolism (i.e., nicotine metabolite ratio (NMR)) and variation in *CYP2A6*; 2) variation in *CYP2B6* and plasma concentrations of bupropion and hydroxybupropion; and 3) variation in social/behavioral variables, including weight concerns, body image, and the presence of other smokers in the home.

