#### 3.2 Primary Study Endpoints

CONFIDENTIAL

This material is the property of the University of Pennsylvania. Do not disclose or use except as authorized in writing by the study sponsor

- Primary smoking status will be assessed using the Timeline Follow-back method (165) and by using carbon monoxide (CO) concentration to biochemically verify the self-report. Participants will be considered to be abstinent if they self-report abstinence (not even a puff

of a cigarette) for  $\geq 7$  days prior to the assessment after 10 weeks of treatment and at 24 weeks post-TQD and have a CO  $\leq 10$  ppm at that time (166-167). As per convention, participants are assumed to be smoking if they self-report to be smoking at the time point, cannot be reached to provide data at the time point, fail to provide a breath sample at the time point, or provide a breath sample at the time point that has a CO concentration  $> 10$  ppm (166).

- For adverse effects, our primary outcome will be the frequency of moderate or severe side effects from a checklist of bupropion-related side effects (derived from completed bupropion studies), as well as those elicited with open-ended questions, through regular obstetrics visits, and assessments triggered by any pregnancy-related complication. Adverse effects will be systematically assessed by study personnel at 5 time points over the course of the 10-week study and can trigger dose reductions or suspension of medication.
- Birth outcomes obtained from labor and delivery records (permission for which will be included in the informed consent form) will include gestational age, overall and spontaneous preterm birth (i.e., at less than 37 weeks), infant birth weight, whether small for gestational age (i.e.,  $< 10^{\text{th}}$  percentile birth weight for gestational age as determined by the Alexander curve), head circumference, Apgar scores, and NICU admissions. Obstetric complications will include type of delivery and delivery and postpartum complications.

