#### 7.1.1. Aim 1:

The primary efficacy analysis (**H1**) is a comparison in week 10 (of treatment) and week 24 post-TQD of CO-confirmed 7-day point prevalence quit rates for the placebo and bupropion groups. For the week-10 comparison, we expect that the quit rates in the placebo and bupropion arms would approximate those reported in bupropion trials in the general population of smokers (i.e., placebo = 21.2%; bupropion = 35.9%, OR = 2.1; ref. 44). A sample of 360 provides 88% power to detect a significant between-group effect. The OR for bupropion treatment is similar at 24 weeks, based on Jorenby et al. (168) and our own data, and results from 10 and 24 weeks are highly correlated ( $\rho > 0.7$ ). Thus, we have 80% power to detect a significant difference between treatment arms.

Safety analyses (**H2**) will examine maternal safety across the 10-week treatment and 24-week follow-up periods and fetal and birth outcomes. Key maternal and fetal outcomes to be compared across treatment groups include rates of moderate-to-severe side AEs of bupropion (from the AE checklist). Key birth outcomes will include Apgar scores, birth weight, duration of pregnancy, rate of obstetrical complications, and need for NICU admission. These analyses will involve a test of equivalence because we cannot use standard statistical tests to conclude that a non-significant comparison shows that the drug is safe (i.e., "the absence of evidence is not evidence of its absence"). In our past study with bupropion, 45% of bupropion-treated participants reported no moderate-to-severe AEs, vs. 47% of participants on placebo, a 2% difference. With the present sample size, we will have 82% power to detect similar equivalence between treatment arms on the frequency of moderate-to-severe AEs over the course of the trial, given that AEs are not significantly different between treatment arms, using an equivalence window of 0.30 to 0.60. Likewise, Oncken et al. (47) reported 38% AEs for the placebo group

CONFIDENTIAL

and 25% in the nicotine group. An equivalence test with placebo and bupropion groups both at 30% and an equivalence window for bupropion of +/-15% provides 81% power.

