**H2:** We will compare treatment arms for equivalence of the frequency of moderate-to-severe AEs (individual and total). The hypothesis test for equivalence is a test of whether the OR is out of the prescribed range for the difference between the treatment arms. Using logistic regression, we will conduct two one-sided tests against predefined upper and lower equivalence boundaries on percent reporting only mild AEs. The test-statistic will be the z-score corresponding to the log of the OR. This provides a more valid test of the potential safety of bupropion for pregnant smokers than a simple comparison of mean responses on a measure of AEs.

**H3:** Mean birth weight will be compared for treatment groups using a two-sample t-test, in the context of multiple linear regression. The regression format allows us to add covariates to adjust for imbalances in participant characteristics between treatment arms. Treatment will be entered as a binary indicator. In a secondary analysis, we will also compare the percentage of participants in each group that delivers an infant of LBW (1500-2500 g) or preterm delivery. These secondary hypotheses will be tested using the z-score corresponding to the OR that will be estimated using logistic regression.

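### The H2 safety hypothesis is not the one tested, and the literal test proportion (only mild AEs) is not the one behind the equivalence window

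*Combined protocol and SAP*

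**What the plan says.** The safety hypothesis and its outcome are worded differently in different places.

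- **Section 2, H2:** "There will be no significant differences between treatment arms in the frequency of severe treatment-related AEs".
- **Section 3.2:** for adverse effects, "our primary outcome will be the frequency of moderate or severe side effects from a checklist of bupropion-related side effects", supplemented by open-ended questions, obstetric visits and assessments after complications. Assessment is at five time points in the 10-week study.
- **Section 7.1.1:** in a past study, "45% of bupropion-treated participants reported no moderate-to-severe AEs, vs. 47% of participants on placebo". Power of 82% is claimed "using an equivalence window of 0.30 to 0.60". A second scenario puts both arms at 30% with a window of 15 points either way and claims 81%. The section covers both treatment and the 24-week follow-up. It also says that a non-significant standard test cannot show that the drug is safe.
- **Section 7.2.2, H2:** the opening sentence plans equivalence of moderate-to-severe AEs. The sentence that specifies the two one-sided tests applies them to "percent reporting only mild AEs". The statistic is a z-score for the log odds ratio (OR), against boundaries called predefined but not given.
- **Section 10.1, AE checklist and severity definitions:** AEs are rated none, mild, moderate or severe, so none and mild are separate ratings.

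**The concern.** There are two faults.

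First, the hypothesis in section 2 is not the hypothesis tested. It differs in severity (severe, against moderate or severe), in attribution (treatment-related, a limit that section 3.2 does not set) and in logic (no significant difference, against equivalence). A report could claim that H2 was supported because a comparison of uncommon events was not significant, which is the inference that section 7.1.1 rules out.

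Second, the sentence an analyst would program names a proportion that, taken literally, is neither the endpoint nor its complement. A woman with no AE has not reported only mild AEs. The window was set around the none-or-mild group. Dropping the symptom-free women leaves a middle category. That category loses women whose events become worse than mild and gains women who move from none to mild, so the two shifts can cancel.

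At stake is the formal maternal safety conclusion for a drug given in pregnancy, on an outcome that section 3.2 calls primary.

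**Working it through.** **Inputs from the documents.** n = 180 per arm (section 5.3); two one-sided tests at 0.025 each, so z = 1.96 (section 7.1); proportions and windows from section 7.1.1; OR-scale test from section 7.2.2.

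**Formula.** With d = bupropion minus placebo and limits L and U:

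P(declare equivalence) = Φ((U − d)/SE − z) + Φ((d − L)/SE − z) − 1

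On the difference scale SE = √[p₁(1 − p₁)/n + p₂(1 − p₂)/n]. On the log-OR scale SE = √[1/(n p₁(1 − p₁)) + 1/(n p₂(1 − p₂))].

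**1. The plan's own figure.** With 47% on placebo and 45% on bupropion, d = −0.02, L = 0.30 − 0.47 = −0.17, U = 0.60 − 0.47 = 0.13 and SE = 0.0525. Each limit is 0.15 from d: 0.15/0.0525 − 1.96 = 0.90, Φ = 0.815, so power is 2 × 0.815 − 1 = 63%. On the log-OR scale it is 68%. The stated 82% does not reproduce under the stated test; one side alone gives 81.5%. This is a separate matter, and the present point does not depend on it.

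**2. Can the literal proportion miss a difference?** The documents give no rate of women with zero AEs, so these rates are assumed.

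| | None | Mild only | Moderate or severe | None or mild |
|---|---|---|---|---|
| Placebo | 20% | 27% | 53% | 47% |
| Bupropion | 5% | 27% | 68% | 32% |

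- *Only mild, ±0.15:* d = 0, SE = √(2 × 0.27 × 0.73/180) = 0.0468; 0.15/0.0468 − 1.96 = 1.245; Φ = 0.893; probability 2 × 0.893 − 1 = 79%.
- *None or mild, ±0.15:* d = −0.15, SE = 0.0509. The lower term is Φ(−1.96) = 0.025 and the upper term is about 1, so the probability is about 2.5%. The assumed difference sits exactly on the limit, so this is the nominal error rate.
- *OR scale*, limits from 0.30 and 0.60 against 0.45: (0.30/0.70)/(0.45/0.55) = 0.524 and (0.60/0.40)/(0.45/0.55) = 1.833. Only mild: OR 1, SE 0.237, probability about 50%. None or mild: OR (0.32/0.68)/(0.47/0.53) = 0.531, probability about 3%.

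**3. What the literal reading does with no drug effect.** Suppose 15 to 25% of women report no AE (assumed). Then only mild is 45% minus that, or 20 to 30%.

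| Rate in both arms | Power, ±0.15 | Power, OR 0.524 to 1.833 |
|---|---|---|
| 20% | 89% | 32% |
| 30% | 75% | 55% |
| 45% (planned) | 63% | 68% |

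Power moves in opposite directions on the two scales.

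**4. The OR limits are not determined.** Window 0.30 to 0.60 gives OR limits 0.524 to 1.833 against a 45% reference, but 0.483 to 1.691 against 47%. The second window (30% ± 15 points) gives 0.412 to 1.909. It follows reported AE rates (38% vs 25%). If 30% is the rate of having an AE, the limits for the AE-free side are the reciprocals, 1/1.909 = 0.524 and 1/0.412 = 2.429.

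**The case against.** The strongest reply is that only mild is shorthand for nothing worse than mild. The same paragraph opens with moderate-to-severe AEs, and excluding symptom-free women would contradict that opening. On this reading the tested proportion is the 45 to 47% one, and the test sentence needs only rewording. This is plausible and cannot be excluded. The literal words and the separate none rating point the other way, and a safety test should not depend on which is guessed.

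It can also be said that the Study Summary and sections 3.2, 7.1.1 and 7.2.2 agree on moderate-to-severe AEs, and that the planned analysis is equivalence, so section 2 is the outlier. That is right. It makes the repair easy, but the stated hypothesis is still not the one tested. Section 3.2 also does not say any cause: it sets no attribution limit, but its checklist is of bupropion-related effects.

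A reader might infer more: that a literal only-mild rate of 20 to 30% falls at or below the 0.30 boundary even with no drug effect, so that the test must fail. The documents do not support this. Section 7.2.2 tests a between-arm OR, which is 1 under no effect at any base rate. The 0.30 to 0.60 window is a margin around a planning rate of 45%, not a floor for an arm's rate. As the third step of the working shows, the base rate only changes power.

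**Conclusion.** The point holds in two parts of different strength. The mismatch between H2 in section 2 and the planned equivalence test is explicit in the text and needs no assumption. The mismatch between only mild AEs and the proportion behind the window holds on the literal reading; on the shorthand reading it is a wording fault.

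The size of the second part rests on assumed rates. In the example, a 15-point difference in moderate-to-severe AEs passes the literal test with probability about 79% (±15 points) or 50% (OR scale), against 2.5 to 3% on the planned proportion. The example shows that the error can happen, not how likely it is.

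On either reading, the plan does not say which window applies or what its OR limits are. It also leaves the assessment period open: 10 weeks of treatment in section 3.2, treatment plus 24-week follow-up in section 7.1.1.

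**What to change.** - **Section 2:** restate H2 as equivalence between arms in the proportion of women with no moderate or severe AE.
- **Section 7.2.2:** replace only mild AEs with that same proportion, and state that women with no AE are included.
- **Sections 7.1.1 and 7.2.2:** name the one window that applies, the reference rate, and the resulting lower and upper OR limits, since the OR is what is tested.
- **Sections 3.2 and 7.1.1:** reconcile the assessment period and state whether any attribution limit applies. Table 2 schedules AE assessment only up to week 10, so a primary endpoint up to week 10 matches the data collected systematically.
- Report severe AEs and treatment-related AEs descriptively by arm.

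The cost is wording plus a decision on the window and its OR limits, made before unblinding. No new data collection is needed. The power statement should be recomputed for the chosen window and scale.

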**Studies of NRT for Smoking Cessation during Pregnancy:** In an effectiveness study (45), pregnant smokers received cognitive-behavioral therapy (CBT) and were randomly assigned to receive a choice of NRT (gum, patch, or lozenge) or no medication. Although the quit rate in the NRT group was approximately double that of the comparison group, the study was stopped because the NRT group had twice the serious adverse event (SAE) rate of the no-medication group. After adjusting for a history of preterm delivery, which was the most common SAE, the difference in SAE rate between groups was not statistically significant ( $p=0.09$ ). Three efficacy studies of NRT have been conducted in pregnant smokers (46-48). In a Danish study (46), all women received counseling and either 6 weeks of a nicotine patch or placebo. At the end of pregnancy, neither quit rates nor mean CPD differed by group. However, patch compliance was poor (i.e., the average use being only 2 weeks). In a US study (47), 194 pregnant smokers were randomly assigned to receive treatment with 2 mg gum or placebo combined with individual behavioral counseling. Smoking cessation rates were non-significantly higher in the NRT group. Importantly, despite limited adherence to NRT, it produced a greater reduction in CPD and cotinine concentrations than placebo and was associated with better treatment retention. Mean (SD) birth weight [3287 g (SD=569) vs. 2950 g (SD=657);  $p<0.001$ ] and mean gestational age [38.9 weeks (SD=1.7) vs. 38.0 weeks (SD=3.3);  $p=0.014$ ] were significantly greater in the nicotine group. In a UK study (48), 1,050 pregnant smokers were randomly assigned to nicotine patch or placebo for 8 weeks, combined with behavioral counseling. Although the quit rate was higher at 1 month in the NRT group (21.3% vs. 11.7% for placebo), the rate of abstinence from the quit date until delivery did not differ significantly (9.4% for NRT and 7.6% for placebo). Importantly, however, adherence was very low. Thus, NRT does not enhance quit rates in pregnant women, possibly due to the higher rate of metabolism (i.e., inactivation) of nicotine in pregnancy and poor medication adherence in the studies.

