### **4.2. Exclusion Criteria**

1. During the last 90 days from screening visit, meets any criteria for a DSM-IV diagnosis of drug or alcohol dependence—excluding tobacco or cannabis dependence and, for methadone or buprenorphine maintenance patients, opioid dependence—**AND** either evidences ongoing use of illicit drugs other than cannabis or continues to abuse or misuse prescription drugs such as CNS stimulants.
2. Pregnant with triplets or higher order multiples
3. Has an unstable psychiatric disorder (i.e., suicide risk moderate or severe, as reflected by a score of  $\geq 9$  on the MINI Section B (Suicidality) or a suicide attempt during the preceding year, psychiatric hospitalization within the last 3 months; current psychotic disorder based on the MINI)
4. Current or past Bipolar Disorder as determined by a study psychiatrist or psychologist based on assessment with the MINI, relevant information from the medical record and, when warranted, direct clinical evaluation.
5. Current, regular use of psychotropic medication, inhibitors of CYP2B6 (e.g., ticlopidine, clopidogrel), inducers of CYP2B6 (e.g., ritonavir, lopinavir, efavirenz), anticonvulsants (e.g., carbamazepine, phenobarbital, phenytoin), beta-blockers (e.g., metoprolol), Type 1C antiarrhythmics (e.g., propafenone and flecainide), drugs that require metabolic activation by CYP2D6 to be effective (e.g., tamoxifen), drugs that lower seizure

CONFIDENTIAL

- threshold (e.g., antipsychotics, tricyclic antidepressants, theophylline, or systemic corticosteroids), levodopa or amantadine

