## 7. Statistical Plan

### 7.1. Power

A power analysis is provided only for the primary aims because the exploratory aim is hypothesis generating. Most of our power calculations were approximated as 2-sided t- or z-tests, with  $\alpha = 0.05$ , using PASS Software (Power and Sample Size, NCSS Software, Kaysville, UT). Equivalence testing was approximated as two one-sided tests, with  $\alpha = 0.025$  each.

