For **H3**, we have very high power. Oncken et al. (47) found a difference in birth weight between groups of 337 g, which yields an effect size  $> d=0.5$ . The power to detect a difference of that magnitude will exceed 99%, and we have 80% power to detect a difference as small as 180 grams. We also have >89% power to detect differences in secondary analyses of the frequency of low birth weight and preterm delivery.

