### **7.2.2. Specific Aim 1: To compare the efficacy of bupropion with placebo for smoking cessation in pregnant smokers.**

For **H1**, we will test for treatment group differences in a binary abstinence outcome that is a repeated measure using a generalized estimating equations (GEE) model with a logit link. Quit rates at the end of week 10 of treatment and 24 weeks post-TQD will represent our primary outcome variables. Medication group (bupropion vs. placebo) and time point (end of week 10 of treatment and 24 weeks post-TQD) will be treated as categorical predictor variables, and the model will predict separate effects of treatment on abstinence at each time point (an interaction). Our initial analyses will be stratified by site, and we will carefully examine the models for differences by site, testing for an overall interaction. We will use baseline depression (PHQ-9 score of 10) to stratify the randomization. The model may include a small number of covariates added to control error or adjust for confounding [e.g., age, history of pre-term delivery, baseline gestational age, daily smoking rate]. Any variables found to be associated with both outcome and treatment assignment will be entered as covariates. In the absence of an overall interaction (by site), we will pool the study population and account for site in the model as a binary predictor. To evaluate the effectiveness of randomization, we will compare summary statistics for participant characteristics in the two study arms. If there is an imbalance in participant characteristics, statistical adjustment will be used to ensure that the initial results were not biased by it.

Because many participants will fail to become completely abstinent, but may show a reduction in smoking, we will examine cigarette consumption as a secondary outcome. The analysis will be similar to the primary analysis, except that we examine the effect of treatment arm on daily cigarette counts using a GEE model with a negative-binomial link. Likewise, time to (recurrent) event models will be fitted using Cox regression, stratified by event sequence, as in Schnoll et al. (52), to assess lapse and recovery events over 24 weeks.

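### Twin pregnancies are eligible, but the birth-weight analysis (H3) neither fixes plurality as a covariate nor says which weight a twin mother contributes

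*Combined protocol and SAP*

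**What the plan says.** **Eligibility.** The only exclusion on plurality in Section 4.2 is "Pregnant with triplets or higher order multiples". Twin pregnancies are therefore eligible. The plan gives no expected number of them.

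**Randomisation.** Section 5.3 stratifies on PHQ-9 score and study site, and on nothing else.

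**H3 analysis (Section 7.2.2).** "Mean birth weight will be compared for treatment groups using a two-sample t-test, in the context of multiple linear regression". On covariates it adds: "The regression format allows us to add covariates to adjust for imbalances in participant characteristics between treatment arms". No covariate is named for H3. The examples offered for the H1 abstinence model are "e.g., age, history of pre-term delivery, baseline gestational age, daily smoking rate"; plurality is not among them. The secondary comparison of low birth weight (LBW) and preterm delivery is expressed as a percentage of participants. For mean birth weight, nothing states whether a twin mother supplies one weight, the mean of two, or two records.

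**Power (Section 7.1.1).** The prior nicotine-gum trial "found a difference in birth weight between groups of 337 g, which yields an effect size" above 0.5, and "we have 80% power to detect a difference as small as 180 grams".

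**Other birth outcomes.** Section 3.2 lists infant-level outcomes (birth weight, head circumference, Apgar scores, NICU admission). Section 7.1.1 puts several of them into the safety comparisons.

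**The concern.** Twins are lighter and are born earlier for reasons unrelated to treatment. Whether a pregnancy is a twin pregnancy is known at enrolment, because the triplet exclusion cannot be applied without it. A strong baseline predictor of this kind would normally be fixed in the model in advance. Here it enters only if someone notices an imbalance.

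Three things follow:

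- The residual variance is larger than it need be.
- The estimate carries an avoidable component from chance differences in twin numbers.
- The analyst has to choose, after the data are in, how a twin mother's two weights are handled. If both were entered as independent observations, the standard error would be too small.

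**Working it through.** **Inputs from the documents**

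- Group size: 180 per arm (Section 5.3).
- Two-sided alpha of 0.05 (Section 7.1: "Most of our power calculations were approximated as 2-sided t- or z-tests").
- SDs from the prior nicotine-gum trial (Section 1.1): "birth weight [3287 g (SD=569) vs. 2950 g (SD=657".

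**Assumed inputs (the documents give none)**

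- Share of twin pregnancies p = 2-4%, which is about 7 to 14 of 360.
- Twin birth-weight deficit D = 600-1000 g.
- The planning SD describes singletons only.

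**Step 1: reproduce the plan's power**

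- Pooled SD = √((569² + 657²)/2) = √377,705 = 614.6 g.
- SE of the arm difference = 614.6 × √(2/180) = 64.8 g.
- Effect size = 337/614.6 = 0.55.
- Difference detectable with 80% power = (1.960 + 0.842) × 64.8 = 181.5 g.
- Power is 79.3% at 180 g and 99.9% at 337 g.

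The stated figures reproduce.

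**Step 2: leave plurality out, one record per mother**

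Total variance = 614.6² + p(1−p)D². The SD of the chance twin contribution to the arm difference = D × √(2p(1−p)/180).

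| p, D | Added variance (g²) | SD (g) | SE (g) | 80%-power difference (g) | Chance-shift SD (g) | Power at 180 g | Power at 337 g |
|---|---|---|---|---|---|---|---|
| no twin term | 0 | 614.6 | 64.8 | 181.5 | 0 | 79.3% | 99.9% |
| 2%, 600 g | 7,056 | 620.3 | 65.4 | 183.2 | 8.9 | 78.6% | 99.9% |
| 3%, 1000 g | 29,100 | 637.8 | 67.2 | 188.4 | 18.0 | 76.3% | 99.9% |
| 4%, 1000 g | 38,400 | 645.1 | 68.0 | 190.5 | 20.7 | 75.4% | 99.9% |

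Adjusting for plurality returns the model to roughly the first row. The gain is about 1 to 4 points of power at 180 g and essentially none at 337 g. The chance-shift SD of 9-21 g is 3-6% of 337 g and 5-11% of 180 g.

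**Step 3: would the imbalance clause catch it?**

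Take 3% twins, about 11 of 360, and suppose they split 3 and 8 between the arms. Fisher's exact test gives p = 0.22; a 2 and 9 split gives p = 0.06. Neither is flagged at 0.05. A split at least as uneven as 3 and 8 occurs by chance about 23% of the time: 2 × (1 + 11 + 55 + 165)/2048 = 0.227. With D = 1000 g it moves the arm difference by (8 − 3)/180 × 1000 = 28 g.

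**Step 4: the unit of analysis**

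If each twin infant were entered as an independent record (3% twins, D = 1000 g, assumed within-pair correlation 0.6), simulation of 20,000 trials under no treatment effect gives type I error of about 6.7% (6.4% in a repeat run) instead of 5%.

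**The case against.** The strongest reply is that the plan already has a remedy. The comparison sits inside a regression; Section 7.2 brings in variables related to treatment arm; Section 7.2.2 promises adjustment if participant characteristics are imbalanced. Moreover, chance imbalance is not bias under randomisation: the t-test's standard error already includes it. Both statements are correct. They answer a charge of bias, but not the loss of precision, and Step 3 shows that an imbalance trigger seldom fires for a characteristic this rare.

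A second reply is that the prior trial's SDs may already include twins, since the documents do not say that it enrolled singletons only. If so, Step 2 counts the twin variance twice. The plan's 181 g would then already carry it, and adjustment would improve on that figure. The size of the gain would be similar and the recommendation would not change.

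Three stronger readings are tempting, and the documents do not support them:

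- **Twin noise rivals the expected effect.** A reader might infer this by comparing it with the 53.9 g in Section 1.1. That figure comes from a meta-analysis of behavioural interventions and is not the H3 planning effect. The ordinary SE of 64.8 g already exceeds it, so twins would not be the main difficulty.
- **Some mothers are counted twice.** Nothing says that each infant is a record. The only unit H3 states, for LBW and preterm delivery, is the participant. The gap is silence about mean birth weight.
- **The test is unadjusted.** It is not: the regression permits covariates. What is missing is advance commitment to this one.

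**Conclusion.** This is a minor specification gap. Twins can enrol, plurality is neither balanced by design nor fixed in the H3 model, and the weight a twin mother contributes is undefined. With one record per mother, the cost is a rise in the 80%-power difference from about 181 g to 183-191 g and a few points of power at most at 180 g. At the planned 337 g, power stays above 99%. These sizes rest on the assumed twin share and deficit and on a planning SD free of twins. The type I error figure of about 6.7% applies only if infants are analysed as independent records, which the plan neither states nor rules out, and it also rests on the assumed within-pair correlation. The H3 power statement itself is sound.

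**What to change.** Add to the H3 paragraph of Section 7.2.2:

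- Plurality (singleton or twin) is a pre-specified covariate in the birth-weight model, whether or not the arms are imbalanced.
- Each mother contributes one record, with the mean weight for twins; alternatively, infants are the records and standard errors are clustered by mother.
- The LBW and preterm models, already per participant, also adjust for plurality. The LBW definition should say how a mother is classified when only one twin is of low birth weight.
- Infant-level outcomes such as NICU admission and Apgar scores follow the same rule on unit and covariate.
- A singleton-only analysis is reported as a sensitivity analysis. Making it primary would drop randomised women for little gain.

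The cost is a few sentences of text. Plurality must already be established to apply the triplet exclusion, so no new visit, measurement or change in eligibility is needed.
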